#### 1.2 Treatment of atopic hand- and foot eczema

Management can be challenging, as delay in adequate treatment and trigger avoidance increase the risk of chronic disease. Symptomatic local therapy includes a stage-adapted application of moisturisers and topical medicaments, and if necessary, antiseptic and anti-inflammatory topical preparations, supplemented by phototherapy and systemic therapy in moderate to severe cases. [23, 24] Systemic therapy is often required for the treatment of moderate to severe chronic HE as indicated by the 5-year follow-up data of the CARPE hand eczema registry (including 35. 8% atopic HE), where up to 39% of all patients with chronic HE were treated systemically. [25] However, evidence from randomized controlled trials on aH&FE is still limited as a recent Cochrane review showed. [26] Despite its high impact, aH&FE is not sufficiently characterized in epidemiological and health care research terms. Particularly, data on real-world efficacy and safety of conventional and biologic treatment modalities, drug survival, burden of disease, care provision and clinically relevant (risk) factors for therapy response, chronicity, disease progression, and prognosis are lacking.

Other relevant research gaps with regard to drug therapy for patients with moderate to severe aH&FE include

- Effectiveness and patient safety studies in everyday care,
- Long-term observations,
- Medical reasons for or against the prescription of systemic therapeutics in patients with moderate to severe aH&FE,
- Treatment sequence and drug survival in everyday care
- Health economic evaluations, and
- Data on patient preferences.

Clinical registries offer an indispensable opportunity to generate information for evidence-based clinical decisions in routine care. [15]

#### 2 STUDY AIMS

#### 2. 1. Primary Objectives

Primary objectives of ReaCT are:

- To establish a science-led clinical registry and research network to investigate the real-world efficacy and safety of conventional and biologic treatment modalities and drug survival in patients suffering from aH&FE
- To register adverse events of systemic treatments in aH&FE

#### Secondary objectives of ReaCT are:

- To investigate patient characteristics, burden of disease and healthcare delivery patterns in patients affected by aH&FE
- To evaluate guideline compliance of diagnostic and treatment procedures among previous and current healthcare providers

#### Exploratory objectives:

- To identify risk factors for disease, disease progression and therapy response in aH&FE
- To identify clinical subtypes and endotypes of aH&FE

#### 3 STUDY DESCRIPTION

#### 3.1 Study design

This is a non-interventional (observatory), prospective clinical register. It gathers data that are routinely collected in the course of clinical diagnostics and therapy of patients with moderate to severe aH&FE, supplemented by questionnaires collected at the visits, without diagnostic, monitoring or therapeutic procedures exceeding usual clinical practice, without additional interventions, and without comparative treatments such as cross-over interventions.

#### 3.2 Study sites

**Study lead:** Study lead is the Department of Dermatology, University Hospital Carl Gustav Carus, Faculty of Medicine at the TU Dresden.

**Registry head office:** The registry head office of the ReaCT registry is the Centre for Evidence-based Healthcare (ZEGV), University Hospital and Faculty of Medicine Carl Gustav Carus, TU Dresden. It is responsible for the coordination of cross-site registry activities, the coordination of the recruitment sites, data management, quality assurance, data storage, data analysis and reporting.

**Recruitment sites:** All dermatological hospitals, outpatient dermatologists with focus on aH&FE/ allergology/ atopic dermatitis in Germany are invited to participate as recruitment sites. The aim is to involve at least 30 recruitment sites. In order to achieve a high representativeness of the results, a mix of specialized sites (e. g. university hospitals and allergy centres) and practices should be achieved. Furthermore, participating sites are encouraged to include as many (consecutive) patients as possible who meet the inclusion criteria. Participating sites are given the opportunity for scientific cooperation. Participation is for scientific reasons. An expense allowance is paid for the documentation of the visits to the recruitment sites.

#### 4 PATIENT POPULATION

#### 4.1 Patients

Adults who refer to dermatology clinics or dermatology practices in Germany with indication for or under systemic therapy due to moderate to severe aH&FE. The registry will include at least 500 patients. The observation period is not limited in time.

#### 4.2 In- and exclusion criteria

#### **Inclusion Criteria**

- 18-100 years of age
- Confirmed diagnosis of AD by U. K. diagnostic criteria for atopic dermatitis (see Appendix 1) [18-20]
- At least moderate AD of either hands or feet assessed with HECSI ≥ 17 [16] and/or FECSI severity score (based on the HECSI) ≥ 17
- Indication of anti-inflammatory systemic therapy for aH&FE, or antiinflammatory systemic therapy for aH&FE conducted within the past 24 months [1]

#### **Exclusion Criteria**

- Insufficient German skills for completion of study questionnaires
- EASI ≥ 16
- Any condition which, in the opinion of the investigator, would not be in the best interest of the participant to participate (e.g. impairment of well-being, incapacitated patients) or which could prevent, limit or defeat the assessments in the protocol.

#### 4.3 Endpoints

#### **Primary Endpoints**

In analogy to the recommendations of the HOME initiative, we consider changes in the following primary endpoints for real-world efficacy of applied therapies:

- Objective severity of clinical signs, in ReaCT measured with HECSI-50, HECSI-75, and HECSI-90 six months after treatment was first prescribed (analogue analyses concerning FECSI)
- Patient-reported symptoms measured with POEM six months after treatment was first prescribed
- Disease control over time measured with RECAP six months after treatment was first prescribed
- Quality of life measured with HEIS six months after treatment was first prescribed
- Another primary endpoint is the safety of applied treatments at each visit.

#### **Secondary Endpoints**

Secondary Endpoints are:

- Impact of applied treatment on primary endpoints: biologics vs conventional treatment
- Impact of potential risk factors on primary endpoints

Evaluation per visit including changes over time:

- Proportion of treatment response and duration of response based on IGA changes
- Disease modification measured as complete remission and number of flares since previous consultation on hands and feet, respectively, HECSI, FECSI, EASI, IGA, RECAP, POEM, DLQI, PGA, WPAI, pruritus NRS, pain NRS, sleep disturbance NRS, Depression CES-D

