#### 5 STUDY COURSE

There will be no study-specific intervention. Included patients will be observed without a patient-related maximum observation time. A baseline visit takes place upon patient inclusion in the registry. Follow-up visits are intended as part of the outpatient visits at the participating centres at 3 months and 6 months after baseline, and then every 6 months to document the course of the therapy. When a new systemic treatment was started (at baseline or later) the following visits take place 4 weeks after first new drug application, then 3 months and 6 months after therapy start, and then every 6 months.

These dates may vary by ±2 weeks. Fig. 1 shows an exemplary visit plan.

[figure not shown]

Figure 1: Visite schedule ReaCT with Baseline-Visit, Follow-Up-Visit, Interim-Visit and 4-Week-Visit; examples illustrate visit schedule with respect to different points in time of initiation of a new systemic therapy (ST)

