#### 5.3 Interim visits

Interim visits may take place between the regular study visits if the treating physician deems this necessary. Reasons for interim visits can be, for example, flares of the disease, the occurrence of ADRs due to the treatment of aH&FE, hospitalization due to aH&FE or a change in the anti-inflammatory systemic therapy.

The physicians' and patients' questionnaires for the interim visits correspond to those for the follow-up visits (see 5. 2, Table 2).

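### The flare endpoint counts events since the last visit, so its value shifts with the visit schedule whenever a new systemic therapy starts

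*Protocol*

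**What the plan says.** Under the heading "Evaluation per visit including changes over time", the secondary endpoints in Protocol section 4.3 include "Disease modification measured as complete remission and number of flares since previous consultation on hands and feet, respectively". The patient form (Table 2) matches: relapses are asked about since the last visit, at every visit except Visit 1.

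Section 5 sets the intervals. Without a new systemic therapy, visits fall at "3 months and 6 months after baseline, and then every 6 months to document the course of the therapy". Once one is started, at baseline or later, they fall "4 weeks after first new drug application, then 3 months and 6 months after therapy start, and then every 6 months". Then: "These dates may vary by ±2 weeks".

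Section 5.3 adds unscheduled visits, which use the same questionnaires as follow-up visits: "Reasons for interim visits can be, for example, flares of the disease". Adverse drug reactions, hospitalisation and a change of systemic therapy are other examples given there.

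Section 7 names t-tests or Mann-Whitney tests for mean differences, and regression and analysis of variance for changes over time. Neither 4.3 nor 7 gives flares a rate, a person-time denominator or an adjustment for interval length.

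**The concern.** A count of events since the last visit is proportional to the time since that visit. Here that time is tied to treatment: it drops to about 4 weeks after a drug start and lengthens to about 26 weeks once therapy is stable. A patient whose flare rate has not changed can therefore record fewer flares per visit just after a switch.

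Interim visits add a second problem. Each one restarts the counting period, and when a flare prompted it, the length of the period depends on the outcome being counted.

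The synopsis lists treatment sequence, drug survival and change of treatment among the primary objectives. Comparisons before and after a switch, or of new with continuing therapy, are natural uses of these data, and they are the ones exposed.

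**Working it through.** **Inputs.** The counting window is the time since the previous consultation (section 4.3, Table 2). Visit times are from section 5, with 3, 6 and 12 months taken as 13, 26 and 52 weeks. The protocol gives no flare rate and no figure for this endpoint, so there is nothing of its own to reproduce; the power calculation in section 7 concerns HECSI-50 response. Assumptions: a constant flare rate, the new drug first taken at about the start visit, and no interim visits.

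**Intervals.**
- New systemic therapy: 4; 13 − 4 = 9; 26 − 13 = 13; 52 − 26 = 26 weeks.
- Unchanged, counted from baseline: 13; 26 − 13 = 13; 52 − 26 = 26 weeks.
- Continuing beyond month 6: 26 weeks each.

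**Ratio of expected counts.** Expected count = rate × weeks / 52. With equal rates the ratio of two counts is the ratio of their intervals, whatever the rate.

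| Visit after new start | Against a 26-week interval | Against unchanged patients from baseline, same month | Against a 13-week interval (switch made at month 3 or 6) |
|---|---|---|---|
| Week 4 | 4/26 = 0.15 | no matching visit | 4/13 = 0.31 |
| Month 3 | 9/26 = 0.35 | 9/13 = 0.69 | 9/13 = 0.69 |
| Month 6 | 13/26 = 0.50 | 13/13 = 1.00 | 13/13 = 1.00 |
| Month 12 | 26/26 = 1.00 | 26/26 = 1.00 | 26/13 = 2.00 |

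The last column shows that the artefact can also run the other way: after a switch at month 3 or 6, the month-12 count doubles with no change in rate.

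**Visit window.** With 2 weeks either way at each visit, the 4-week interval can be 2 to 6 weeks and a 26-week interval 22 to 30. The week-4 ratio then lies between 2/30 = 0.07 and 6/22 = 0.27.

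**Absolute size, for assumed rates of 1, 2 and 4 flares per year.**
- Expected flares over 4 weeks: 0.08, 0.15, 0.31. Over 26 weeks: 0.50, 1.00, 2.00.
- Probability of at least one flare, 1 − exp(−rate × weeks / 52): 7%, 14%, 26% over 4 weeks; 39%, 63%, 86% over 26 weeks.

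**Averaging over all visits in 52 weeks, at an assumed 2 per year.**
- New start, 4 visits: 2/4 = 0.50 per visit.
- Unchanged from baseline, 3 visits: 2/3 = 0.67.
- Continuing, 2 visits: 2/2 = 1.00.

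The new-start mean is 0.75 of the second and 0.50 of the third. Per patient-time all three are 2.0 per 52 weeks, so the difference disappears once the count has a time base.

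**The case against.** The strongest reply is that the protocol states no flawed analysis. Evaluating per visit says when data are summarised and names no estimator. An analysis plan could supply the count model and the denominator, and section 7 calls the work descriptive and explorative. This holds for the choice of model. It does not rescue the endpoint, because the protocol itself fixes what is counted, and over what period, without a unit of time.

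The reply has more force against four stronger readings that a reader might infer:

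- **That biologics are favoured over conventional treatment.** The restarted schedule applies to any new systemic therapy, so starters of both kinds have the same intervals at the same visit. The declared contrast is also on the primary endpoints, which do not include flares. Pooling all visits would distort it only if the groups differ in their share of new starts, and no such pooling is stated.
- **That every new start shows a spurious fall.** Relapses are not recorded at Visit 1, so a patient starting therapy at baseline has no earlier registry count to fall from. The 26-week comparator is the most extreme of those tabulated.
- **That safety is biased in the same way.** The protocol says "Another primary endpoint is the safety of applied treatments at each visit", but section 6.6 records reactions as events with start and end dates, not as counts since the last visit. The direction is open: short intervals lower a per-visit figure, while closer observation or early clustering of reactions can raise it.
- **That severity and patient-reported scores are affected by interval length.** POEM, RECAP, DLQI and the itch and sleep scales have fixed recall periods. They are exposed only if interim visits are mixed into time-point summaries. The protocol does not say that they will be, and visit type is recorded.

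**Conclusion.** The concern holds for the flare endpoint. As written, it measures flare rate multiplied by time since the last visit, and that time depends on when therapy was started. At a constant rate, new starts show 0.15, 0.35 and 0.50 of the count over a preceding 26-week interval at week 4, month 3 and month 6; against unchanged patients counted from baseline, only month 3 differs among matched visits (0.69). These ratios need no assumption about the flare rate, but they do assume nominal visit times and no interim visits. The effect of flare-triggered visits comes on top and cannot be sized from the document.

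The distortion is confined to comparisons of new with continuing treatment and to comparisons before and after a switch made after baseline. It does not reach biologic against conventional starters at the same visit. For safety, only the absence of a stated time base can be noted, with no claim about direction. This is a secondary, exploratory endpoint, but the artefact is large for such comparisons and cheap to remove.

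**What to change.** In sections 4.3 and 7:

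- **Flares.** Define the endpoint as a rate per patient-time on the current therapy. Sum the flares reported at all visits, interim visits included, over fixed windows from therapy start, for example 0–6 and 6–12 months. Analyse with a Poisson or negative binomial model with log person-time in the window as offset. An offset for each between-visit interval is not enough, because a flare-triggered visit makes the interval depend on the outcome; a fixed window largely avoids this.
- **Adverse drug reactions.** As an accompanying clarification, report them per exposure time, using the recorded start dates.
- **Severity and patient-reported scores.** Summarise time courses at scheduled visits counted from therapy start, but keep an interim visit at which a therapy is started as that therapy's baseline. Excluding all interim visits would lose the starting value for those patients.

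No new data are needed: visit date, visit type and reaction dates are already collected. The cost is slightly more analysis work and a rule for partial windows (drop-out, or a further switch before the window closes), which contribute only their observed person-time.

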#### 5 STUDY COURSE

There will be no study-specific intervention. Included patients will be observed without a patient-related maximum observation time. A baseline visit takes place upon patient inclusion in the registry. Follow-up visits are intended as part of the outpatient visits at the participating centres at 3 months and 6 months after baseline, and then every 6 months to document the course of the therapy. When a new systemic treatment was started (at baseline or later) the following visits take place 4 weeks after first new drug application, then 3 months and 6 months after therapy start, and then every 6 months.

These dates may vary by ±2 weeks. Fig. 1 shows an exemplary visit plan.

[figure not shown]

Figure 1: Visite schedule ReaCT with Baseline-Visit, Follow-Up-Visit, Interim-Visit and 4-Week-Visit; examples illustrate visit schedule with respect to different points in time of initiation of a new systemic therapy (ST)

#### 5.1 Patient recruitment, Visit 1 (baseline/inclusion in the register)

A prerequisite for the inclusion of patients in the registry is appropriate information about the purpose of the study, the procedure, possible risks and benefits of participation in the study. Information about the study is provided in person by the attending physician and in writing in the patient information leaflet. Only after all the patient's questions have been clarified will the patient be asked to sign **two** copies of the consent form. The patient is then given a copy of the patient information/informed consent form. Patients who fulfil the inclusion criteria can be included in the study after providing written informed consent.

Physician questionnaire (Table 1): During the baseline visit, the general and specific medical history, the physical examination with documentation of the skin findings (HECSI, FECSI, EASI, global disease severity (IGA for hand and feet, respectively), the documentation of typical lesions and the documentation of the previous therapy as well as the therapy prescribed from this visit onwards and the reasons for this therapy decision are documented first. Adverse events and possible adverse drug reactions (ADR) of the aH&FE therapy are also recorded using the physician questionnaire.

Patient questionnaire (Table 2): Patients are asked to complete the patient questionnaire, which records information on sociodemographic characteristics, disease history, quality of life (DLQI, HEIS), symptoms (POEM, NRS itching, pain and sleep disturbances, peak itch), current

skin findings (PGA for hand and feet, respectively; RECAP disease control), occupational restrictions due to atopic dermatitis (WPAI), depressive symptoms (CES-D) and treatment satisfaction.

The questionnaires are provided by the REDCap database.

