Disease severity in the past 3 days or 24 h - NRS for itching, pain, sleep disturbances*,†	0	0	0
Patient involvement in treatment decisions*	0	0	0
Assessment of severity of the moderate to severe aH&FE - current (PGA), NRS on disease control in the past 12 weeks*	0	0	0
Disease severity in the past week - RECAP**,† (separately for hand and foot eczema)	0	0	0
Dermatological quality of life - DLQI**,†	0	0	0
Hand eczema-related quality of life - HEIS**,†	0	0	0
Patient Oriented Eczema Measure - POEM**,† (separately for hand and foot ec- zema)	0	0	0
Depression CES-D**,†	0	0	0
Work Productivity and Activity Impairment Questionnaire - WPAI**,† (separately for hand and foot eczema)  * Questionnaire developed by ReaCT team based on questionnaire	0	0	О

\* Questionnaire developed by ReaCT team based on questionnaires applied in the TREATgermany registry (EK TUD 118032016)

\*\* Validated outcome measurement instrument

† See p. 26ff for details

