#### 5.2 Follow up visits

At each follow-up visit (see Figure 1 for the visit schedule), the physician documents the clinical examination findings (HECSI, FECSI, EASI, global disease severity (IGA)), the prescribed therapy including the rationale for the prescription, as well as reasons for changing or continuing therapy and possible adverse drug reactions (ADRs).

The patient questionnaire for follow-up visits is analogous to the questionnaire for baseline visits (see Table 2).

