#### 6.4 Data capture, data protection and data security

All clinical and patient-reported data are entered into an electronic data entry system specially developed for the ReaCT registry. A REDCap (Research Electronic Data Capture) database is used for this purpose. [27, 28]

REDCap is a secure, web-based software platform designed to support data capture for research studies, providing 1) an intuitive interface for validated data capture; 2) audit trails for tracking data manipulation and export procedures; 3) automated export procedures for seamless data downloads to common statistical packages; and 4) procedures for data integration and interoperability with external sources.

The physician enters clinical data browser-based on a PC or other terminal device. The corresponding questionnaire for the patient is opened on an iPad/mobile device using a QR-Code that is created from the physician's data-recording system. The patient enters their data webbased into the REDCap database using the iPad/mobile device. This ensures that the patient cannot view any data other than the questionnaire they are working on (neither their own previously entered data nor the physician's treatment data or data from other patients).

Data is primarily entered directly into this database. Alternatively, data can also be collected with a paper version of the questionnaires and later documented in the REDCap database if electronic data entry is not possible at the site.

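### Section 5.1 most naturally places the baseline POEM, RECAP and HEIS after the therapy decision, and sections 5.2 and 5.3 state no order

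*Protocol*

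**What the plan says.** Section 5.1 (Visit 1) describes the physician questionnaire, then the patient questionnaire. The physician part covers history, examination with HECSI, FECSI, EASI and IGA, previous therapy and the new prescription. It closes with "the therapy prescribed from this visit onwards and the reasons for this therapy decision are documented first". The next paragraph has the patient complete the instruments, including HEIS, POEM and RECAP.

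Section 6.4 says how the patient form is reached: "The corresponding questionnaire for the patient is opened on an iPad/mobile device using a QR-Code that is created from the physician's data-recording system". It adds that the patient cannot see on the device "neither their own previously entered data nor the physician's treatment data or data from other patients".

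Section 5.2 lists the physician's entries at follow-up without a sequence word. On the patient side it says: "The patient questionnaire for follow-up visits is analogous to the questionnaire for baseline visits". Section 5.3 refers back to 5.2. Neither section says which form comes first.

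Table 2 in the visit schedule includes the item "Patient involvement in treatment decisions" at baseline and at later visits.

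Section 4.3 defines the primary efficacy endpoints as changes, read six months from first prescription: clinical signs (HECSI response), symptoms (POEM), disease control (RECAP) and quality of life (HEIS). Its first secondary endpoint compares biologics with conventional treatment on these endpoints.

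**The concern.** When an outcome is a change from a patient-reported starting value, that value should be obtained before anything at the visit can colour it. If a site follows 5.1 as it most naturally reads, a patient who is about to start a systemic drug rates symptoms, control and quality of life after the prescription has been made. Prescribing normally involves telling the patient. Relief at being offered a new drug could lower the scores, and a wish to justify the need for it could raise them.

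Three of the four efficacy domains depend on this reading. Expectation may also differ between patients given a biologic and those given a conventional drug, which is the comparison in section 4.3. A baseline score cannot be collected again later, so the order has to be settled in advance.

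**Working it through.** **1. Is an order stated?**
- Baseline (5.1): yes, on the natural reading. The word first closes a list that covers nearly the whole physician form, including the new prescription, and the patient form follows in the next paragraph. No linking word such as then makes the order explicit.
- Follow-up and interim visits (5.2, 5.3): no. The likeness in 5.2 refers to the content of the questionnaire and points to Table 2.
- QR code (6.4): no. It comes from the physician's system, but nothing says the therapy section must be filled in first.

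**2. Would the patient know the drug?** The protocol does not say so. The display rule in 6.4 governs what appears on the device, not what is said in the consultation. Knowledge of the choice is therefore a plausible inference. The Table 2 item on treatment decisions fits it, although that item may also concern earlier decisions.

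**3. How would a shift carry through?** Let Y0 be the true pre-treatment score, Y6 the month-6 score, and d the shift in the recorded baseline score caused by knowing the drug.
- Recorded change within a group: Y6 − (Y0 + d) = (Y6 − Y0) − d. The whole of d enters the change, with opposite sign.
- Difference in mean change, biologic minus conventional, with shifts dB and dC: the error is −(dB − dC). Equal shifts cancel in the comparison but stay in each group's change.
- If the analysis adjusts for baseline with slope b, the error in the comparison is −b(dB − dC).

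**4. Can d be given a number?** No. The protocol has no data on the effect of form order. The competing mechanisms point in opposite directions, so the sign is open too. Section 6.5 gives 1.3 points as a meaningful improvement in HEIS, but no shift to set against it. It gives no such threshold for POEM or RECAP.

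**5. Does the sample-size statement depend on this?** No. Section 7 uses physician-rated HECSI-50 against a 50% reference. With a two-sided 5% level (assumed, since sidedness is not stated), 80% power and no continuity correction, the smallest d satisfying n = [1.96·√(2p̄(1−p̄)) + 0.84·√(p1(1−p1)+p2(1−p2))]² / d², with p1 = 0.50, p2 = 0.50 + d and p̄ their mean, is 26.7%, 19.3% and 13.8% for n = 50, 100 and 200 per group. The protocol states 27%, 19% and 14%. Form order does not enter this calculation.

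**6. Can the form always come before the examination?** Not at Visit 1. Inclusion needs HECSI and/or FECSI of at least 17 and an indication for, or recent use of, systemic therapy. EASI of 16 or more excludes, and written consent comes first. The examination may therefore have to precede the form, but the discussion of the specific drug need not.

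**The case against.** The strongest reply is that the protocol fixes very little here. In 5.1, the word first may mean order within the physician form, because the next sentence adds that adverse events are recorded as well. POEM and RECAP ask about the past week or seven days, which leaves less room for a reaction to today's news. All analyses are descriptive or exploratory (section 7). These points stand as limits on the weight of the concern. They do not remove it: the text is at best ambiguous, a fixed recall period reduces but does not exclude a shift, and section 6.5 states no recall period for HEIS.

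A reader might infer more than the documents support:
- **That month-6 answers follow the physician's verdict by design.** Sections 5.2 and 5.3 state no order. This can happen but is not prescribed.
- **That form order is why outcomes are reported with knowledge of the drug.** This is an unblinded registry of routine care. Patients know their drug at month 6 in any order.
- **That the QR code enforces physician first.** It is compatible with either order.
- **That new starters are biased relative to patients who continue treatment.** The endpoints are anchored at a first prescription, and the stated comparison is biologics with conventional treatment.
- **That the bias can be expressed as a share of the 1.3-point HEIS threshold.** Any shift put into that ratio would have no source in the protocol.

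**Conclusion.** The point holds in a limited form. Section 5.1 most naturally has the baseline patient questionnaire completed after the new therapy and its reasons are documented, and 5.2 and 5.3 leave the order open. For patients who start a drug at that visit, the pre-treatment reference for three patient-reported primary endpoints may be given with knowledge of the choice.

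This rests on three assumptions: that sites follow the order as it reads, that the choice is discussed with the patient when it is made, and that the Visit 1 score serves as the pre-treatment reference for a drug started then. Size and direction are unknown. The HECSI endpoint and the detectable differences in section 7 are not affected. It is a modest procedural weakness that is easily avoided, and worth correcting because the lost baseline reading cannot be recovered.

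**What to change.** - **Section 5.1:** replace the present order with a statement that, after consent and the eligibility check, the patient completes the questionnaire before the choice of therapy is discussed.
- **Sections 5.2 and 5.3:** state that the questionnaire is completed before the physician's examination and therapy discussion, in particular at visits where a systemic therapy is started and at the month-6 visit.
- **Table 2:** ask only the item on "Patient involvement in treatment decisions" afterwards.
- **Section 6.4:** say that the QR code is available once the visit record is opened, and that the REDCap audit trail will be used to check the order of entry. The trail cannot show when the drug was discussed, and for paper forms typed in later it does not show when they were completed. Those sites rely on the instruction.

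The cost is protocol wording, a site instruction, a small change in visit flow and a short second patient page, which means handing over the device a second time. No additional visits or instruments are needed.
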